2.1. Primary endpoint

Primary endpoint of the study is the proportion of CD patients achieving steroid-free clinical-practice-deep remission (CPDR) after 12 months from baseline of treatment with Risankizumab, defined as the combination of:

patient reported outcomes (PRO) (patients reported abdominal pain \leq 1 and average stool consistency \leq 5 on Bristol Stool Scale without use of oral/intravenous steroids (prednisone-equivalent or budesonide) in the last 3 months)

AND an objective parameter of inflammation:

Faecal calprotectin <150 mcg/g, OR SES-CD \leq 4 and at least a 2-point reduction vs baseline and no subscore >1 in any individual variable, OR transmural healing at MRI/CT scan enterography or intestinal ultrasound, defined as BWT \leq 3 mm with no signs of active disease.

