2.2. Secondary endpoints

1. Percentage of patients achieving the CPDR of CD after 6 and 24 months of risankizumab.
2. Percentage of patients achieving clinical remission of CD (defined as HBI < 5) after 3 months, 6 months, 12 months and 24 months of risankizumab.
3. Percentage of patients showing clinical response of CD (defined as a reduction of the HBI of at least 3 points from baseline) after 3 months, 6 months, 12 months and 24 months of risankizumab. This endpoint will be assessed only in patients with an HBI > 5 at baseline.
4. Percentage of patients achieving endoscopic remission of CD (defined as SES-CD \leq 4 and at least a 2-point reduction vs baseline and no subscore >1 in any individual variable) after 3 months, 6 months, 12 months and 24 months of risankizumab.
5. Percentage of patients showing endoscopic response of CD (defined as a greater than 50% decrease in SES-CD from baseline (or for isolated ileal disease and a baseline SES-CD of 4, at least a 2-point reduction from baseline) after 3 months, 6 months, 12 months and 24 months of risankizumab.
6. Percentage of patients achieving the steroid-free “deep remission” of CD, defined as the combination of clinical remission and endoscopic remission according to the above-mentioned criteria (PMID: 26303131) after 6 months, 12 months and 24 months of risankizumab.
7. Percentage of CD patients achieving transmural healing at CT-scan or MRI enterography or at intestinal ultrasound (defined as a BWT \leq 3 and normal parietal contrast enhancement or color Doppler signal (CDS) or absence of hyperemia) after 3 months, 6 months, 12 months and 24 months of risankizumab.
8. Percentage of patients showing response of CD at radiological exams, including CT-scan or MRI enterography and intestinal ultrasound (defined as a decrease in BWT by 25% from baseline or 2.0 mm, or greater than 1.0 mm with a decrease in parietal contrast enhancement or in CDS assessed by the modified Limberg score of one grade) after 3 months, 6 months, 12 months and 24 months of risankizumab.

9. Variation of C-reactive protein (CRP) after 3 months, 6 months, 12 months and 24 months of treatment with risankizumab in CD patients.
10. Identification of clinical, endoscopic or radiologic predictors of deep remission in CD at 12 months and 24 months.
11. Percentage of patients achieving control of extraintestinal manifestation at 3 months, 6 months, 12 months and 24 months.

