The evaluation of the difference in terms of CPDR at 12 months and 24 months, respectively, according to the different biological sequential therapies at II and III lines will be evaluated by Kaplan-Meier survival analysis. In particular, the log-rank test will be applied and appropriate cumulative incidence curves will be drawn. The analysis will be performed using the R packages “*ggplot2*” and “*survminer*” [31,32].

Potential predictors of CPDR will be assessed by Cox regression models. In detail, the potential predictors of the outcome will be evaluated by means of ordinary proportional hazards Cox regression models, and the Hazard Ratios (HR) and the 95% confidence intervals (CIs) will be reported. The proportionality of the hazard functions will be evaluated by visual inspection of the hazards and Schoenfeld residual plots. In case of doubtful proportionality, Cox weighted regression models will be

fitted. The analysis will be performed with "*survival*" and "*coxphw*" R packages [33-37]. Whether possible due to the different sample sizes of each therapeutic line and sequential strategy, to evaluate the combined effects between drug and line of administration, multivariable interaction models will be fitted, one per each predictor, and the interaction hazard ratios (IHR) reported. In summary, the coefficients of the main effects (in exponential terms) will be interpreted as HRs of the outcome by considering a unit increase of the predictor in the reference category (first line) (HR_{predictor}) as for quantitative predictors, whilst as increase in the hazard of the outcome occurring, as compared with the (arbitrarily) chosen reference group for qualitative data. The interaction parameters (IHR) will be interpreted as difference (in HR terms) of variations of the predictors among the different lines (first line as reference category).

5. Study procedures

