5.1. Experimental procedures

Data will be retrieved from the electronic archives of all participating center. Each patient will be identified by a number who will avoid double insertion of the same patient and will ensure the anonymization of data. Collected data will be entered in an electronic case report form (RedCap) and will follow all the requirements of Italian privacy policy.

In depth, the standard points will be: induction of therapy (T0 - week 0); 12 weeks after the beginning of therapy (T1), 6 months after the beginning of therapy (T2), 12 months after the beginning of therapy (T3), and 24 months after the beginning of therapy (T4).

The following clinical data at each time-point will be collected, to calculate Harvey Bradshaw Index – general well-being, abdominal pain, number of liquid/soft stools, abdominal mass and extraintestinal manifestations for CD.

Endoscopic or radiologic monitoring of disease activity respectively by ileocolonoscopy or intestinal ultrasound or CT-scan or MRI-enterography will be collected at baseline and at 12 and 24 months after the start of therapy. Endoscopic disease activity will be assessed according to the SES-CD.

Steroid-free clinical practice deep remission (CPDR) will be defined based on patient reported outcomes (PRO) combined with an objective parameter of inflammation:

- patients reported abdominal pain ≤ 1 and average stool consistency ≤ 5 on Bristol Stool Scale without use of oral/intravenous steroids (prednisone-equivalent or budesonide) in the last 3 months;

AND

- Faecal calprotectin <150 mcg/g, OR SES-CD \leq 4 and at least a 2-point reduction vs baseline and no subscore >1 in any individual variable, OR transmural healing at MRI/CT scan enterography or intestinal ultrasound, defined as BWT \leq 3 mm with no signs of active disease.

6. Ethical aspects

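### Therapy lines and predictors are analysed by time to first CPDR, although the endpoint is the proportion in CPDR, a reversible state, at months 12 and 24

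*Protocol*

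**What the plan says.** Section 2.1 states: "Primary endpoint of the study is the proportion of CD patients achieving steroid-free clinical-practice-deep remission (CPDR) after 12 months from baseline". The definition combines symptom scores, a steroid condition ("without use of oral/intravenous steroids (prednisone-equivalent or budesonide) in the last 3 months") and an objective marker of inflammation. Section 2.2 adds, as endpoint 1, "Percentage of patients achieving the CPDR of CD after 6 and 24 months of risankizumab". Endpoint 12 compares second, third and fourth line use on the primary endpoint. Endpoint 10 is "Identification of clinical, endoscopic or radiologic predictors of deep remission in CD at 12 months and 24 months", where deep remission is the separate composite of clinical and endoscopic remission in endpoint 6.

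Section 4.4 sizes the study on a two-sided 95% confidence interval for a single proportion and calls the primary evaluation descriptive, by therapy line. For the contrast between lines it changes method: the CPDR difference at 12 and 24 months "according to the different biological sequential therapies at II and III lines will be evaluated by Kaplan-Meier survival analysis", with log-rank test and cumulative incidence curves. It then says "Potential predictors of CPDR will be assessed by Cox regression models", reporting hazard ratios, Schoenfeld residual plots and, if needed, weighted Cox models. It gives no definition of the event time, no rule for a patient who reaches CPDR and later loses it, and no censoring rule. The chi-squared and exact tests in the same section are assigned to baseline differences and to adverse events.

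Section 5.1 fixes the time points at baseline, 12 weeks, and 6, 12 and 24 months.

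**The concern.** CPDR is a state that a patient is in or out of at a visit. It rests on present symptoms, the last three months of steroid use and an objective marker, and section 1 describes the disease as relapsing and remitting, so it can be gained and lost. A Kaplan-Meier curve of first CPDR cannot fall when patients relapse. It answers how many have ever reached CPDR by a given month, whereas the endpoint asks how many are in CPDR at that month.

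Two things are at stake. First, a reader will compare the curves at months 12 and 24 with the reported proportions, and the curves will be at or above them. Second, the log-rank and Cox contrasts weigh early attainment and ignore durability. Two lines with the same 12-month rate can look different because one gains CPDR and loses it more often. The only stated method for comparing CPDR between lines therefore does not address endpoint 12. For predictors there is a further mismatch: the models are written for CPDR, while endpoint 10 names deep remission.

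**Working it through.** **1. The plan's own figure.** Section 4.4 gives an interval width of 0.28945 for n = 50 and a proportion of 0.5. The exact (Clopper-Pearson) interval for 25/50 is 0.35527 to 0.64473, width 0.28945, which matches. The Wald (0.27718) and Wilson (0.26711) widths do not. The precision calculation is thus for a proportion at one time. For the expected 200 patients at 50%, the exact interval is 0.4287 to 0.5713, width 0.1427, half-width about 7.1 points.

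**2. State at a visit against ever reached.** Let p6, p12 and p24 be the shares in CPDR at each visit, and r the probability that a patient in CPDR is still in CPDR at the next visit. Only the 50% for p12 comes from the protocol (its scenarios are 50%, 55% and 60%). The values p6 = 0.40, p24 = 0.50 and r are assumptions, and nobody stops treatment.

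- Gain between months 6 and 12: q = (p12 − p6·r)/(1 − p6)
- Ever by month 12: E12 = p6 + (1 − p6)·q = p12 + p6·(1 − r)
- Gain between months 12 and 24, taken as equal for patients never in CPDR and those who lost it: g = (p24 − p12·r)/(1 − p12)
- Ever by month 24: E24 = E12 + (1 − E12)·g

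For r = 0.8: q = (0.50 − 0.32)/0.60 = 0.30 and E12 = 0.40 + 0.60 × 0.30 = 0.58; g = (0.50 − 0.40)/0.50 = 0.20 and E24 = 0.58 + 0.42 × 0.20 = 0.664.

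| r | True, months 12/24 | 1 − KM, months 12/24 | Excess in points |
|---|---|---|---|
| 1.0 | 50% / 50% | 50% / 50% | 0 / 0 |
| 0.9 | 50% / 50% | 54% / 59% | 4 / 9 |
| 0.8 | 50% / 50% | 58% / 66% | 8 / 16 |
| 0.7 | 50% / 50% | 62% / 73% | 12 / 23 |

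A simulated Kaplan-Meier analysis (200 patients, 2,000 runs) gave 57.9%/66.4% at r = 0.8 and 61.9%/73.4% at r = 0.7, in agreement.

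**3. Sensitivity.** The 12-month excess is p6·(1 − r), whatever p12 is. For r = 0.9, 0.8 and 0.7 it is 3, 6 and 9 points with p6 = 0.30, and 5, 10 and 15 points with p6 = 0.50. With p6 = 0.40 it passes the 7.1-point half-width once r falls below 1 − 0.071/0.40, about 0.82.

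**4. Contrast between lines.** Take two lines, each at 50% at month 12, with an assumed 100 patients per line. If one has r = 1.0 (ever 50%) and the other r = 0.8 (ever 58%), a comparison of ever-by-12 proportions is significant in about 20% of studies. With r = 0.7 (62%) it is about 40%. The 12-month endpoint is equal in both cases.

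**5. Stopping, if stoppers were censored.** This is an assumption, since no rule is stated. Suppose 20% of patients not in CPDR stop after each visit, with r = 0.8. Kaplan-Meier still reads about 58%/66%. The share in CPDR at month 12, with stoppers counted as failures, is 0.40 × 0.8 + 0.60 × 0.8 × 0.30 = 0.464; at month 24 the simulation gives about 44%.

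**The case against.** The strongest reply is that the primary result is safe. It is a descriptive proportion with a single-proportion interval, by line, and nothing in the Kaplan-Meier plan alters it. That stands. A reader might infer that the study's headline remission rate is inflated; the protocol does not support this. Only rates read from the curves and the log-rank and Cox contrasts are at issue.

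It can also be said that the event might be meant as CPDR at the month-12 visit itself. With nobody censored earlier, 1 − KM would then equal the proportion. But all events would share one nominal time, the curve would be a single step, and the planned proportional-hazards checks would have nothing to examine. The text does not say this, and those checks point to time to first CPDR.

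Four stronger readings are tempting and should not be drawn:

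- That patients who stop risankizumab are censored. No rule is stated, and such a rule may sit in an analysis plan not at hand.
- That a large overstatement is certain. It is zero if nobody loses CPDR, and the protocol gives no relapse, stopping or 6-month rate for risankizumab. The loss of response quoted in section 1 concerns TNF inhibitors.
- That the hazard ratios merely reflect visit dates. Visits are nominally common to all patients, so Cox regression with tied times approximates a discrete-time model of first CPDR. That is a coherent quantity, but a different one.
- That the comparison is confounded because later lines are sicker. The protocol does not state this link, and it plans multivariable interaction models involving line.

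**Conclusion.** The point holds for the comparison of lines (endpoint 12) and for the predictor models (endpoint 10). The protocol names a method that does not estimate the quantity its endpoint defines, and this is stated in the current text rather than left open. The direction follows from the definitions: with first CPDR as the event and no stopping, 1 − KM is at or above the visit proportion. The size is not known. Over the assumed range of 100% to 70% retention between visits, with 40% in CPDR at month 6, it is 0 to 12 points at month 12 and 0 to 23 points at month 24, against a half-width of about 7 points at 200 patients. Censoring of stoppers, if adopted, would widen the gap to a proportion that counts them as failures. The modelling of CPDR where endpoint 10 names deep remission is a smaller mismatch that the same rewording can settle.

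**What to change.** Reword section 4.4 as follows:

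- Analyse CPDR at month 12, and separately at month 24, as a binary outcome.
- Compare lines (endpoint 12) and assess predictors by logistic or modified-Poisson regression with baseline covariates, reporting risk differences or ratios with 95% confidence intervals.
- For this analysis, count patients who stopped risankizumab before the visit as not in CPDR, and add a sensitivity analysis for missing visits. The present imputation text covers missing values only below 5%, which may not suffice for data taken from archives.
- Fit the same model for deep remission, which endpoint 10 names.
- Keep Kaplan-Meier and Cox for true time-to-event outcomes such as time on drug, or label them explicitly as time to first CPDR.

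The cost is rewording; the visit data are already to be collected, although the reason for and date of stopping must be retrievable. The displayed rates may be less favourable, and the timing of first remission is no longer the main contrast.

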4.4. Sample size evaluation and statistical analysis

Based on the real-life study design and on the primary endpoint, which foresees a descriptive evaluation of remission rates according to each therapy line considered, we present diverse scenarios of potential sample size (from 50 till 300 by 25), and related confidence intervals in order to detect a CPDR at 12 months of 50-55 and 60% according to the evidence available from the current literature on the drugs under investigation. All scenarios are assessed according to a single group study design with a two-sided 95% confidence interval for a single proportion. A table with all potential scenarios will be provided as attachment.

As an example, such single-group design to obtain a two-sided 95% confidence interval for a single proportion, assuming a sample proportion of 0.5, with a sample size of 50, would produce a confidence

interval width of 0.28945, i.e., 0.5 ± 0.145 . The confidence interval widths were computed using PASS 2022, version 22.0.4 [29].

Based on the data available to the participating centers (for the retrospective phase) and the recruitment capabilities of the centers during the enrollment period, we expect to enroll 200 subjects with Crohn disease in this retrospective study.

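### Section 4.4 compares CPDR between lines by Kaplan-Meier, calls the curves cumulative incidence and names no competing-event method; if exits before CPDR are censored, the share reaching CPDR is overstated

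*Protocol*

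**What the plan says.** Protocol section 4.4 sets the target of the line comparison as "The evaluation of the difference in terms of CPDR at 12 months and 24 months, respectively", and says that it "will be evaluated by Kaplan-Meier survival analysis. In particular, the log-rank test will be applied and appropriate cumulative incidence curves will be drawn". Predictors of CPDR are to be examined with "ordinary proportional hazards Cox regression models". The only alternative offered is weighted Cox regression, for doubtful proportionality.

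The primary endpoint in section 2.1 is of another kind. It is the "proportion of CD patients achieving steroid-free clinical-practice-deep remission (CPDR) after 12 months from baseline", a simple proportion at a fixed time. Secondary endpoint 12 in section 2.2 compares second, third and fourth line on that same primary endpoint.

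The protocol names no competing event and gives no censoring rule. It does not say how a patient enters the curves who stops risankizumab, has surgery or dies before CPDR.

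**The concern.** In most survival analyses the event is unfavourable. Here it is favourable, so leaving treatment without the event will often mean that treatment has failed. Death makes CPDR impossible, and stopping for failure or intolerance makes it impossible on that course of risankizumab. Both are competing events.

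Censoring such a patient assumes that he or she would later have reached CPDR at the same rate as those who stayed. One minus Kaplan-Meier then estimates what would happen if nobody ever left, not the cumulative incidence that section 4.4 promises. It also fails to estimate the kind of quantity that endpoint 12 refers to, which is a share of all patients treated. The excess depends on how many leave, so lines with different exit rates would be shifted by different amounts.

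**Working it through.** **The plan's own figure.** Section 4.4 gives a "two-sided 95% confidence interval for a single proportion", "assuming a sample proportion of 0.5, with a sample size of 50", with an "interval width of 0.28945, i.e., 0.5 ± 0.145". The exact (Clopper-Pearson) interval for 25/50 runs from 0.35527 to 0.64473, a width of 0.28945, so the figure reproduces. It is the precision of a plain proportion and uses no Kaplan-Meier estimate. The point below does not touch it.

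**Inputs.**
- p, the share of all patients reaching CPDR by 12 months: 50%, 55% and 60%, the planning rates in section 4.4 ("in order to detect a CPDR at 12 months of 50-55 and 60" per cent).
- d, the share with a competing exit before CPDR by 12 months: not in the protocol, so assumed at 10%, 20% and 30%.
- Exits are censored. This is also an assumption.

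**Model (a), constant hazards.** The total hazard accumulated over 12 months is H = −ln(1 − p − d), and CPDR has the fraction p/(p + d) of it. With exits censored:

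1 − KM = 1 − (1 − p − d)^(p/(p + d))

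For p = 0.50 and d = 0.20: 1 − 0.30^(0.50/0.70) = 0.577.

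**Model (b), visit-based extreme.** All exits come before the month-12 visit and all CPDR is recorded at it:

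1 − KM = p/(1 − d)

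For the same inputs: 0.50/0.80 = 0.625. The Aalen-Johansen estimate returns p in both models.

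| True p | d = 10%, (a) / (b) | d = 20%, (a) / (b) | d = 30%, (a) / (b) |
|---|---|---|---|
| 50% | 53.4% / 55.6% | 57.7% / 62.5% | 63.4% / 71.4% |
| 55% | 58.9% / 61.1% | 63.8% / 68.8% | 70.7% / 78.6% |
| 60% | 64.4% / 66.7% | 70.1% / 75.0% | 78.5% / 85.7% |

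The excess over p is 3 to 4, 8 to 10 and 13 to 19 points in model (a), and 6 to 7, 13 to 15 and 21 to 26 points in model (b).

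**A count example.** Of 200 patients, 60 reach CPDR at month 6 and 30 more at month 12, so the true share is 90/200 = 45%. Let 20 patients (10%) leave before month 6 and 20 (10%) between months 6 and 12. Then 1 − KM = 1 − (1 − 60/180)(1 − 30/100) = 53.3%.

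**Effect on the line comparison.** Take line II at p = 55%, d = 10% and line III at p = 50%, d = 30%. Model (a) gives 58.9% against 63.4%, so the line with the lower CPDR share looks better. The cause-specific hazard ratio, III against II, is ln(1 − 0.634)/ln(1 − 0.589) = 1.13. With line III at d = 20% instead, model (a) keeps the true order (58.9% against 57.7%) and model (b) reverses it (61.1% against 62.5%).

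Exits in line III above which the order reverses, with 10% exits in line II:

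| True CPDR, II v III | Model (a) | Model (b) |
|---|---|---|
| 55% v 50% | 22% | 18% |
| 60% v 50% | 31% | 25% |
| 55% v 45% | 34% | 26% |

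In these scenarios the worse line needs about 8 to 24 points more exits than the better one.

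**The case against.** The strongest reply is that the protocol never says that exits are censored. Kaplan-Meier does not force it: a patient who leaves can be kept at risk without an event, and then the excess disappears. A statistical analysis plan could set that rule without contradicting section 4.4. Nor does the protocol say that observation ends when the drug is stopped. Section 5.1 collects archive data at fixed times, and section 3.2 allows up to 24 months per subject. No section says that surgery precludes CPDR. All of this stands, and it makes the finding conditional.

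The reply is also right on the tests. With exits censored, log-rank and Cox validly compare cause-specific hazards, which is a legitimate target for predictors. The mistake would be to read them as differences in the proportion reaching CPDR.

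Three stronger readings are tempting, and the document does not support them:
- **That the order of lines will reverse.** The protocol gives no exit rates for risankizumab, none by line, and no split of the 200 patients. Its failure figures in section 1 concern TNF inhibitors. Reversal is possible, not expected.
- **That the inflation is always largest in the line with most failures.** This holds at equal CPDR rates only. In model (a), p = 45% with d = 20% inflates by 6.7 points, and p = 60% with d = 15% by 7.0.
- **That the primary result is biased.** It is a proportion at 12 months and does not use these curves.

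What the reply does not remove is that section 4.4 names the estimator, test and model, promises cumulative incidence, and has nothing in it to prevent the default.

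**Conclusion.** The point holds in conditional form. If exits before CPDR are censored, the curves in section 4.4 are not cumulative incidences and lie too high for any non-zero exit rate. The sizes above rest on assumed exit rates, on constant hazards or the visit-based extreme, and on taking the planning rates as the share who reach CPDR by 12 months. Unequal exits would distort the line comparison of endpoint 12, by an amount the document does not allow one to estimate. The predictor analysis needs a correct interpretation rather than a different model. The consequence is confined to these secondary analyses. The change is still worth making, because it replaces the named estimator with a standard one that delivers what the protocol says it will show.

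**What to change.** In section 4.4, choose one of two routes for the line comparison:

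1. Define stopping for failure or intolerance, and death, before CPDR as competing events. Estimate cumulative incidence by Aalen-Johansen and compare lines by Gray's test. State explicitly whether surgery is counted.
2. Compare lines on the 12- and 24-month proportions, with exits counted as non-CPDR. This is closest to the primary endpoint, which endpoint 12 invokes.

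Keep Cox for predictors, described as a cause-specific hazard model whose hazard ratios are not differences in the share reaching CPDR. Fine-Gray regression can be an optional addition. Reserve censoring for administrative end of follow-up. Keeping exits at risk without event to month 24 is equivalent to route 1 only if all other patients have complete 24-month follow-up. If some are administratively censored earlier, it over-weights the failures and understates incidence.

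The cost is a few sentences and standard R functions, with no change to the sample size. Exit dates and reasons must be coded, and the curves will be lower than under censoring.

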12. Comparison between the efficacy of risankizumab, as assessed according to the primary endpoint of the study, when used as second, third or fourth line of biological treatment.
13. Assessment of the safety of risankizumab during the entire study period.

3. Study design and investigational plan

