4.3. Exclusion criteria

1. Age < 18 years.
2. Patients with diagnosis of indeterminate IBD.
3. Patients naive to advanced (biological or small molecule) therapy for IBD.
4. Refusal to sign written informed consent certifying the willingness of the subject to participate to the study.

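### The line-of-therapy interaction models take first line as reference although eligibility leaves no first-line patients, and the stated log-rank test omits the fourth line named in endpoint 12

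*Protocol*

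**What the plan says.** Three parts of the protocol bear on line of therapy.

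- **Who can enter.** Section 4.2, item 3, requires failure of at least one advanced therapy, biological or small molecule. Section 4.3, item 3, excludes "Patients naive to advanced (biological or small molecule) therapy for IBD". Section 3.1 repeats the requirement of prior failure. Every patient starts risankizumab.
- **Which lines are to be compared.** Secondary aim 12 and secondary endpoint 12 (section 2.2) compare risankizumab on the primary endpoint "when used as second, third or fourth line of biological treatment".
- **How line is analysed (section 4.4).**
  - Remission rates are to be described for each line.
  - CPDR at 12 and 24 months is to be compared "according to the different biological sequential therapies at II and III lines" by Kaplan-Meier curves and a log-rank test.
  - Ordinary Cox models for predictors of CPDR come next, with no mention of a reference line.
  - Interaction models follow, under the condition "Whether possible due to the different sample sizes of each therapeutic line and sequential strategy". Their purpose is given as "to evaluate the combined effects between drug and line of administration, multivariable interaction models will be fitted, one per each predictor". The main effect of a quantitative predictor is read by "considering a unit increase of the predictor in the reference category (first line"; a qualitative predictor is read against an arbitrarily chosen group. The interaction hazard ratios (IHRs) are "interpreted as difference (in HR terms) of variations of the predictors among the different lines (first line as reference category".

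**The concern.** The reference line of the interaction models is one that the eligibility criteria rule out. A hazard ratio in an empty group, and ratios relative to that group, have no data behind them. Someone has to choose another reference when the model is run. In a retrospective study that choice would be made with the outcomes already in hand, and the interpretation printed in the protocol would no longer describe the output.

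The protocol also uses three different sets of lines: two to four in endpoint 12, two and three in the log-rank test, and first line as the anchor of the Cox interactions. Endpoint 12 therefore has no stated test that covers all of its groups. Finally, the interaction models are said to address drug and line together, yet only one drug is studied and the word is not defined.

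**Working it through.** **The plan's own figure.** The only computed figure in section 4.4 is the 95% confidence interval width for a proportion of 0.5 with n = 50. The exact (Clopper-Pearson) interval for 25 of 50 runs from 0.35527 to 0.64473, a width of 0.28945, as stated. Nothing below depends on it.

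**Inputs.** Lines two, three and four (endpoint 12); no first-line patients (sections 4.2 and 4.3); 200 expected subjects (section 4.4); one study drug (sections 3.1 and 4.2).

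**Predictor-by-line model with first line as reference.** Let x be a quantitative predictor and L2, L3, L4 the indicators of lines two to four:

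log h(t) = log h0(t) + g2·L2 + g3·L3 + g4·L4 + b·x + d2·x·L2 + d3·x·L3 + d4·x·L4

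Here exp(b) is the hazard ratio of x in first line, and exp(d2), exp(d3), exp(d4) are the IHRs against first line. There are 7 coefficients. With nobody in first line, two identities hold for every patient:

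1. L2 + L3 + L4 = 1. The sum is constant and is absorbed by the baseline hazard, so only the differences g3 − g2 and g4 − g2 can be estimated.
2. x·L2 + x·L3 + x·L4 = x, so only the sums b + d2, b + d3 and b + d4 can be estimated.

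Estimable combinations: 2 + 3 = 5. Shortfall: 7 − 5 = 2. Neither b nor any single d is identified. A numerical rank check on a simulated design of 200 patients spread over lines two to four agrees: 7 columns, rank 5. The even spread was an assumption; the rank does not depend on it provided each line holds several patients.

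**Same model with second line as reference.** The columns are L3, L4, x, x·L3 and x·L4: 5 columns, rank 5. Everything is estimable. The main effect becomes the hazard ratio of x in second line, and the IHRs compare lines three and four with it.

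**The word drug.** If it means the study drug, it takes one value. A literal drug-by-line model then has rank 2 out of 7 columns (first line as reference) or 2 out of 5 (second line as reference): only the two line contrasts survive. The protocol does not write out such a model, so this shows only that the word needs a meaning other than the study drug if it is to stay.

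**Lines covered.**

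| Place | Lines |
|---|---|
| Aim 12 and endpoint 12 | second, third, fourth |
| Section 4.4, descriptive rates | each line considered |
| Section 4.4, log-rank test | second, third |
| Section 4.4, interaction models | not listed; first as reference |

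The log-rank test leaves out 1 of the 3 groups in endpoint 12, and no analysis in section 4.4 names the fourth line.

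**The case against.** The best defence is that this is a labelling slip in an optional, secondary analysis. The text already describes one model per predictor, with effects varying by line, and that model is sound once an existing line is the reference. An analyst would probably use second line without being told. This stands as a limit on severity. It does not make the written definitions correct, and the opening condition concerns small groups, not a group that eligibility makes empty.

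A second defence is that the zero depends on how lines are counted. Eligibility counts biologics and small molecules together; endpoint 12 counts biological treatment. A patient who failed only a small molecule could be called first line for biologics. That is possible, but endpoint 12 lists no first line and the protocol defines no such group. The point shows that the count needs stating; it does not rescue the reference.

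Third, the log-rank sentence speaks of sequential therapies and is not expressly tied to endpoint 12, and descriptive rates by line are promised. Both are true. A reader might infer that fourth-line patients go unreported; the descriptive provision says otherwise. What is missing is a stated test that includes them.

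A reader might also infer that a drug-by-line term has been specified and must fail. The text does not support that: no drug coefficient is defined, the word appears only in the statement of purpose, and the nearby mention of sequential strategy suggests that it may mean the prior drug or sequence, which does vary.

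**Conclusion.** The point holds, at moderate severity. If line counts all advanced therapies, as eligibility does, the stated reference category contains 0 of 200 expected patients. The first-line hazard ratio of a quantitative predictor and all IHRs against first line are then not estimable as defined. The log-rank comparison omits one of the three lines in endpoint 12. The documents do not give the number of fourth-line patients, so the share of the cohort left out of the test is unknown.

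It would go too far to conclude that the Cox analysis cannot be run, or that every hazard ratio is affected. The ordinary predictor models carry no reference line, and main effects of qualitative predictors are read against a separately chosen group. The primary endpoint, the confidence-interval calculation and the expected enrolment do not change.

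**What to change.** In section 4.4:

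1. Name second line as the reference category in both places where first line now appears, for the quantitative main effects and for the IHRs.
2. Extend the Kaplan-Meier/log-rank comparison to second, third and fourth line, matching aim and endpoint 12.
3. State whether line counts all advanced therapies, as in sections 4.2 and 4.3, or only biologics, as endpoint 12 says, and use that count throughout.
4. Delete drug from the purpose of the interaction models, or define it as the prior drug or sequence.

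The cost is a wording change. No extra patients are needed and no sample-size figure moves. It should be made before the line comparisons are run.
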